Weaning From Mechanical Ventilation in Neurological Patients

NCT03128086

Date: March 3, 2017

INTRODUCTION

A high percentage of patients with acute neurological disease require invasive mechanical ventilation (MV) to isolate the airway, to provide adequate oxygenation and to prevent aspiration of gastric content (1-3). During weaning from MV, a spontaneous breathing trial (SBT) is realized before extubation in order to assess patient's capacity to breath (4-6), and reducing the risk of extubation failure. The extubation failure is associated with a prolonged length of stay in the intensive care unit (ICU) and in the hospital, as well as, more risk of infections and higher mortality (7). In neurological patients, a successful SBT can not predict exactly the success of extubation (8-10). It is necessary both the assessment of muscle strength and the ability to keep the airway clearance capacity to ensure success of extubation (8-15).

The results obtained with the application of weaning protocols in neurological patients are not conclusive (16), with the exception of one clinical trial (17). A meta-analysis concluded that the establishment of weaning protocols in subjects in a medical-surgical unit reduced the duration of MV by 25%, weaning time by 78% and ICU stay by 10%. These results support the use of weaning protocols in patients undergoing MV (18).

In this study we try to demonstrate that the use of a protocol-directed weaning in neurological patients will reduce the rate of extubation failure and associated complications. The primary objective is to reduce the failure rate of extubation. As secondary objectives we are going to analyse the incidence of infections, need for tracheostomy, duration of MV, length of ICU and hospital stay, and mortality at ICU, hospital and 90 days.

MATERIAL AND METHODS

A prospective interventionist no randomized study will be conducted in a medical-surgical ICU. Patients 18 years or older with acute medical or surgical neurological disease [acute ischaemic or haemorrhagic stroke, acute subarachnoid haemorrhage, traumatic brain trauma, metabolic encephalopathy (toxic, infectious as encephalitis or meningitis), scheduled neurosurgical surgery with a prolonged MV, and status epileptics], will be included. Exclusion Criteria: scheduled neurosurgical surgery (duration of MV <24 hours), neuromuscular disease,

spinal cord injury, tracheostomized, inability to be evaluated, severe multiple traumatic injuries evaluated by the Injury Severity Score (19), direct extubation and self-extubation, patients who died during their ICU stay (without a trial of weaning), and patients transferred to another hospital.

At ICU admission, the following variables will be collected: age, sex, body mass index, comorbidities, prognosis severity scale by Simplified Acute Physiological Score (SAPS) 3, Organ failure by Sequential Organ Failure Assessment (SOFA) (at ICU admission and 5 days after admission), reason for MV, the level of consciousness by Glasgow Coma Scale (GCS) at the time of intubation and where it was performed. During the ICU stay, all neurological treatments and procedures such as treatment of intracranial hypertension (mannitol or hypertonic saline, hyperventilation, decompressed craniotomy), cranial tomography (CT) scanner, external ventricular drainage, intracranial pressure sensor, cerebral arteriography, will be collected. The infectious complications (ventilator-associated pneumonia, tracheobronchitis, urinary tract infection, bacteraemia,) will be registered during the ICU stay.

To be included into study, subject undergoing mechanical ventilation will meet the following conditions: no or minimal sedation (propofol \leq 1mg/kg/h o midazolam \leq 0,1mg/kg/h), with spontaneous ventilatory stimulus, absence of intracranial hypertension, Glasgow Coma Score (GCS) $>$ 9 (motor $>$ 4 points), noradrenaline \leq 0,2mcgr/kg/min, (fraction of inspired oxygen)FiO₂ \leq 0.5 (positive end-expiratory pressure) PEEP of 5cmH₂O, no intervention scheduled in the next 48 hours, maximal inspiratory pressure (MIP) $<$ -20cmH₂O (20), occlusion pressure (P_{0.1}) $>$ 6mmHg with support pressure of 7cmH₂O and 0 cmH₂O of positive end-expiratory pressure (Z-PEEP).

Protocol study (study group). The subject will be connected to MV in a pressure support ventilation (PSV) mode, which will be gradually reduced (until a level de pressure support of 10 cmH₂O above 5 cmH₂O of PEEP). After, the subject will be disconnected from the ventilator and a SBT will begin through the connexion of the subject to a T-tube and a source of oxygen (21). Haemodynamic parameters [systolic blood pressure (SBP), heart rate (HR)], and respiratory parameters [respiratory rate (RR), partial pressure of carbon dioxide (paCO₂), partial pressure of oxygen to fraction of inspired oxygen ratio (paO₂/FiO₂), and pH through blood gas analysis and saturation of oxyhemoglobin (SaO₂) by pulse oximetry], and neurological parameters (means by GCS) will be collected during final period of pressure support ventilation (before disconnection) and at onset (5 minutes) and final (between 30 to 120 minutes) of SBT (22). A once daily SBT will be established in all the subjects until they

were extubated. A failure SBT will be considered with more than 2 criteria: $\text{paO}_2 < 50$ - 60 mmHg with $\text{FiO}_2 \leq 0.5$ (or $\text{SaO}_2 < 90\%$), $\text{paCO}_2 > 50 \text{ mmHg}$, $\text{pH} < 7.35$, $\text{RR} > 35 \text{ bpm}$, $\text{HR} > 140 \text{ bpm}$, $\text{SBP} > 180 \text{ mmHg}$, cardiac arrhythmias during SBT, dyspnea, and increased use of accessory muscles (6). If the SBT fails, the subject will reconnect to MV. A successful SBT is defined as absence of whatever of variables above defined. *Airway clearance capacity*. Otherwise, if the SBT is successful, the ability to maintain airway will be analysed by the following variables: Number of aspirations of secretions/8-h nursing shift (No pass-0, 1 pass-1, 2 passes-2, ≥ 3 passes-3), cough capacity (strong -0, mild-1, weak-2, absent-3), appearance of secretions [viscosity (liquid-0, frothy-1, thick-2, dry-3) and colour of secretions (clear- 0, brown- 1, yellow-2, green-3), and finally, the presence of gag reflex (strong- 0, moderate- 1, weak- 2, absent- 3). A score ≤ 8 was considered as adequate to keep the permeability of airway (4). Then the subject will be extubated and connected to venturi mask with FiO_2 of 0.4. In case of extubation failure, the patient will be reintubated. The use of non-invasive ventilation is not considered in this study (neither prevention of extubation failure nor in case of extubation failure).

Conventional weaning (control group). Subjects in the control group will receive weaning from MV according to the usual procedure, by reducing level of PSV. Then a SBT will be performed through a T-tube (the same parameters as protocol study will be collected) and subsequent extubation of the patient if there is a successful SBT. The criteria for SBT and for extubation failure are the same than in the study group. In case of extubation failure, non-invasive ventilation will be not considered, but it left to the discretion of the attending physician.

STATISTIC ANALYSIS. Based upon previous results (10), the authors considered that the need for an intubation could be reduced by 13% (6) [26% in the control group vs. 13% in the study group]. The estimated sample size was 109 patients in each group (confidence interval $[1-\alpha] = 95\%$ ($P=0.05$) and power $[1-\beta] = 80\%$). A comparative analysis was conducted by using the Student's t-test or the Mann-Whitney test for a comparison of the quantitative variables for the parametric and non-parametric characteristics, respectively. For the qualitative variables, we used the Chi-Square statistic or Fisher's exact test. A statistical significance was reached if $P < 0.05$. The cumulative probability of survival was compared by using a Kaplan-Meier estimation of survival and a Log-Rank Test to compare both of the groups. Intention-to-treat

analysis will be realized. The data will be analysed with the aid of the statistical package SPSS 22.0.

REFERENCE

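### Intention-to-treat is promised, but the plan states no rule or time for placing a patient in a group, so there is no recorded assignment to analyse by

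*Combined protocol and SAP*

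**What the plan says.** MATERIAL AND METHODS opens with the design: "A prospective interventionist no randomized study will be conducted in a medical-surgical ICU". One set of entry conditions then applies to everyone: "To be included into study, subject undergoing mechanical ventilation will meet the following conditions: no or minimal sedation", followed by respiratory drive, consciousness, vasopressor dose, oxygenation and inspiratory-strength criteria.

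The two groups are defined by what is done to them. For the study group: "The subject will be connected to MV in a pressure support ventilation (PSV) mode, which will be gradually reduced", then a T-tube SBT and, if that succeeds, an airway-clearance score before extubation. For the control group: "Subjects in the control group will receive weaning from MV according to the usual procedure, by reducing level of PSV", then a T-tube SBT and extubation if it succeeds.

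STATISTIC ANALYSIS gives a target of "26% in the control group vs. 13% in the study group" with 109 patients per group. It lists t-test or Mann-Whitney, chi-square or Fisher, and Kaplan-Meier with log-rank, and closes with the analysis principle: "Log-Rank Test to compare both of the groups. Intention-to-treat" analysis is to be carried out. That principle is named but not defined.

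**The concern.** Intention-to-treat means analysing each patient in the group to which he or she was assigned, whatever happened next. It needs an assignment that is made at a known time and recorded. Non-randomised studies can have one, for example by calendar period, bed or team. This plan states none.

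Two routes to bias stay open. The group could be set after the patient's readiness has been seen. A patient could also be classified afterwards by the pathway followed, which is what intention-to-treat is meant to prevent. Either would let prognosis differ between groups before any effect of the protocol, and the planned tests would read that difference as a treatment effect. Bedside impressions of airway protection are a plausible basis for choice, and the INTRODUCTION itself treats airway clearance as necessary for successful extubation.

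**Working it through.** **Step 1. What the text gives on assignment**

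| Question | Where one would look | Answer in the plan |
|---|---|---|
| Randomised? | MATERIAL AND METHODS, first sentence | No |
| Rule for entering the study group? | Protocol study (study group) | None; procedures only |
| Rule for entering the control group? | Conventional weaning (control group) | None; procedures only |
| When is the group fixed, and by whom? | All sections | Not stated |
| What is known at inclusion? | Entry conditions | Sedation, GCS, FiO2/PEEP, MIP, P0.1 |
| Set for intention-to-treat? | STATISTIC ANALYSIS | Named, not defined |
| Adjustment for prognosis? | STATISTIC ANALYSIS | None planned |

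The methods text runs on without a break, so removed text does not explain the gap. A related point: some exclusions depend on events after admission ("direct extubation and self-extubation, patients who died during their ICU stay (without a trial of weaning), and patients transferred to another hospital"). If they were applied after assignment, they too would conflict with intention-to-treat. The plan does not say when they apply.

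**Step 2. The plan's own figure, used here only as an input**

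For 26% vs 13% and 80% power, the unpooled formula is n = (z_alpha + z_beta)² × [0.26×0.74 + 0.13×0.87] / 0.13².

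- One-sided 5%: (1.645 + 0.842)² × 0.3055 / 0.0169, which gives 112, close to 109.
- Two-sided 5%: (1.960 + 0.842)² × 0.3055 / 0.0169, which gives 142.

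Sidedness is not stated. That is a separate matter; below I take 109 per group as given and assume a two-sided 5% test.

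**Step 3. How far could imbalance alone move the result?**

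From the plan: 109 per group, 26% failure, chi-square test. Assumed, and not in the documents: no true effect; half of all patients at higher risk; a risk ratio R of higher to lower risk between 1.5 and 4.2; higher-risk shares h of 40% vs 60% or 35% vs 65% (study vs control).

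- Lower-risk failure: L = 0.26 / (0.5 + 0.5R). Higher-risk failure: H = R × L.
- Group failure: h × H + (1 − h) × L.
- Spurious difference: (h_control − h_study) × (H − L).
- False-positive rate: the sum of the binomial probabilities of all pairs of counts (109 per group) for which the uncorrected chi-square exceeds 3.84. With no imbalance this gives 5.2%.

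| R | L | H | 40/60: difference | 40/60: false positives | 35/65: difference | 35/65: false positives |
|---|---|---|---|---|---|---|
| 1.5 | 20.8% | 31.2% | 2.1 points | 7% | 3.1 points | 8% |
| 2 | 17.3% | 34.7% | 3.5 points | 9% | 5.2 points | 14% |
| 3 | 13.0% | 39.0% | 5.2 points | 14% | 7.8 points | 26% |
| 4.2 | 10.0% | 42.0% | 6.4 points | 19% | 9.6 points | 37% |

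Hand check of the last cell by normal approximation:

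- Rates: 0.65×0.42 + 0.35×0.10 = 0.308 and 0.35×0.42 + 0.65×0.10 = 0.212.
- Null SE: √(2×0.26×0.74/109) = 0.0594, so the critical difference is 1.96×0.0594 = 0.1165.
- SE under these rates: √((0.308×0.692 + 0.212×0.788)/109) = 0.0591.
- Φ((0.096 − 0.1165)/0.0591) = Φ(−0.35), about 36%, in line with 37% by enumeration.

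Against the 13-point target, spurious differences at 35/65 run from 3.1/13 = 24% to 9.6/13 = 74%. If higher-risk patients went to the study group instead, the same shifts would work against the protocol and hide a benefit.

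**The case against.** The strongest reply is that silence is not evidence of bad practice. Non-randomisation is openly declared and is not an error in itself. Consecutive periods, or a bed or team rule, would fit the text as well as bedside choice does. This stands: the point is that the rule and its timing are unstated.

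Three stronger readings are tempting, and the documents do not support them.

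- **That clinicians choose the arm, or that the pathway followed defines the group.** No section says either. The text only fails to exclude them.
- **That a study patient whose airway check is omitted cannot be told from a control.** The study group also has a stated pressure-support end point before the SBT, where the control text gives no level. The wording on non-invasive ventilation differs too: not considered in the study group, left to the attending physician in the control text. The airway score is the main difference but not the only one.
- **That nothing can be done at analysis.** SAPS 3, SOFA and GCS are collected, and GCS during the SBT falls under the parameters shared by both groups, so partial adjustment is possible. It would be incomplete: cough, secretions and gag appear only in the study-group description, and the shared-parameters remark is attached to the SBT.

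The size is also open to challenge. The documents give no risk ratio between more and less ready patients. The shared entry conditions, and the successful SBT required before extubation in both groups, may narrow the spread of risk. The direction of any steering is unknown. These limits are why a range is shown.

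**Conclusion.** The point holds as a gap in the plan: intention-to-treat is promised without a stated assignment, a time at which it is fixed, or a record of it. Adjustment can partly address imbalance, but it cannot supply the missing assignment record. The plan therefore leaves group choice after readiness is known, and reclassification by pathway, both possible, with unadjusted tests to receive the result.

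The size is illustrative. A modest imbalance (40/60) with a 1.5-fold risk barely moves the error rate, to about 7%. A larger imbalance (35/65) with a 4.2-fold risk takes it to about 37%. Every figure in that range rests on assumed risk ratios and shares, and none of them shows that imbalance did or would occur. If a suitable rule already exists in practice, writing it down and logging the group resolves the point. It should be settled before enrolment.

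**What to change.** In MATERIAL AND METHODS, add:

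1. An assignment rule that is fixed in advance and independent of the attending physician's view of the patient, such as calendar blocks of fixed length, or bed or team at ICU admission. Individual randomisation is not required.
2. A log of every eligible patient, with the assigned group entered before the first SBT, and a statement of whether the event-dependent exclusions apply before or after that entry.

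In STATISTIC ANALYSIS, define intention-to-treat as analysis by the logged group whatever pathway was followed. As a complement, pre-specify adjustment for recorded baseline variables (SAPS 3, SOFA, GCS) and acknowledge that it is incomplete while airway items are not clearly recorded in controls.

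**Cost.** Protocol wording and a simple log, with less discretion for the attending physician. The rule has its own weaknesses. Predictable blocks leave room to time readiness around a change of block, which the log reveals only partly, and bed or team may track severity. A calendar, bed or team rule also brings period or cluster effects, which must be reported and allowed for in the analysis. Whether that would call for more than 109 per group cannot be settled from the documents.

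### Exclusions for direct extubation, self-extubation and transfer have no time limit, so as written they can remove entered patients despite the stated intention-to-treat analysis

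*Combined protocol and SAP*

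**What the plan says.** **Exclusions.** In Material and Methods, the exclusion list closes with "direct extubation and self-extubation, patients who died during their ICU stay (without a trial of weaning), and patients transferred to another hospital". The bracket limits the death criterion to patients who never had a weaning trial. Direct extubation, self-extubation and transfer carry no limit.

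**Entry.** The same section says "To be included into study, subject undergoing mechanical ventilation will meet the following conditions" and then lists readiness conditions for weaning. It gives no time at which a patient counts as entered or is assigned to a group.

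**Allocation.** "A prospective interventionist no randomized study will be conducted in a medical-surgical ICU". The method of assignment is not described.

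**Outcomes.** In the Introduction, "The primary objective is to reduce the failure rate of extubation". The secondary outcomes include "length of ICU and hospital stay, and mortality at ICU, hospital and 90 days".

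**Analysis.** Under Statistic Analysis the principle is "Intention-to-treat", followed by "analysis will be realized". No analysis population is defined, and there is no rule for patients who self-extubate, are extubated directly or are transferred.

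**The concern.** Entry is tied to readiness for weaning in a patient who is still ventilated. Self-extubation, direct extubation (undefined in the protocol; taken here as extubation without a spontaneous breathing trial, SBT) and transfer can all happen after that point. A site that follows the list literally would then drop a patient who was ready, had begun weaning and was being managed in one of the groups. An intention-to-treat analysis would keep that patient.

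Two sets of outcomes are exposed:

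- **Primary outcome.** A self-extubated or directly extubated patient may need reintubation, and the need for reintubation is what the sample size rests on. Removing such patients changes both numerator and denominator.
- **Hospital and 90-day outcomes.** A patient with a known extubation result who is later transferred would leave the primary analysis as well as hospital stay and "mortality at ICU, hospital and 90 days".

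Losses may also differ by group. After a successful SBT the study group must reach an adequate airway-clearance score before extubation, while controls are extubated after a successful SBT. Staff follow a scripted sequence in one group and usual procedure in the other. Either difference could change how often an excluded event occurs.

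**Working it through.** **Plan's own figures.** The plan has no figure for exclusions, so there is none to reproduce. The inputs taken from it are the 26% control failure rate, the 13% study rate and 109 per group (Statistic Analysis). As a check on 109, the unpooled formula n = (z_alpha + z_power)^2 × [0.26×0.74 + 0.13×0.87] / 0.13^2 gives:

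- one-sided 0.05, 80% power: (1.645 + 0.842)^2 × 0.3055 / 0.0169 = 111.8, so 112, within 3% of 109;
- two-sided 0.05, 80% power: (1.960 + 0.842)^2 × 0.3055 / 0.0169 = 141.9, so 142.

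Sidedness is a separate matter. Here 109 serves only as a group size.

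**Reading the sections together.**

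1. Entry requires a ventilated patient who meets the readiness conditions.
2. Three exclusions are in-stay events with no limit before entry.
3. The analysis is stated to be intention-to-treat.

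Items 2 and 3 agree only if the exclusions stop at entry, and nothing in the documents says that they do. This conclusion needs no rates.

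**Size, by assumption.** Let p be the true failure rate among all entered patients, x the fraction of a group dropped after entry and q the failure risk among those dropped. Then

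- rate in those kept = (p − xq) / (1 − x);
- distortion = p − (p − xq)/(1 − x) = x(q − p)/(1 − x).

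The distortion is zero when q = p. Take p = 26% in both groups (no true effect) and losses from one group only. The chance of P<0.05 uses a two-sided normal approximation with 109 against 109(1 − x) patients.

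| x | q | Rate in those kept | Spurious difference (points) | Chance of P<0.05 |
|---|---|---|---|---|
| 5% | 40% | 0.24/0.95 = 25.3% | 0.7 | 5.2% |
| 10% | 50% | 0.21/0.90 = 23.3% | 2.7 | 7.2% |
| 20% | 40% | 0.18/0.80 = 22.5% | 3.5 | 8.6% |
| 20% | 60% | 0.14/0.80 = 17.5% | 8.5 | 29.2% |

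With 109 in a group, 5-20% is about 5 to 22 patients.

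**Direction.** With the planned 26% and 13%, x = 10% and q = 50%:

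- loss from the study group only: (13 − 5)/90 = 8.9%, so the difference becomes 26 − 8.9 = 17.1 points;
- loss from controls only: (26 − 5)/90 = 23.3%, so the difference becomes 23.3 − 13 = 10.3 points.

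The planned 13-point effect can therefore be inflated or diluted.

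**Equal loss.** With the same x, q and p in both groups, both rates move alike and no spurious difference arises. Precision still falls: at 26% and 13%, two-sided power at 109 per group is 68%, and it drops to 66% with 5% lost from each group and to 58% with 20% lost.

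**The case against.** The strongest reply is that the list is meant for screening. Patients already tracheostomized are excluded in the same list, while need for tracheostomy is a secondary outcome, so that item makes sense only before entry. The death criterion covers patients who never reached a weaning trial. Read alike, the direct-extubation, self-extubation and transfer criteria describe patients who left before weaning began, and intention-to-treat is untouched. This reading is plausible and may be what the sponsor meant. It does not settle the point, because the three criteria have no limit and the time of entry is undefined.

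A reader might infer more than the documents support:

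- **That entered patients will certainly be removed and the result is biased.** The text allows this but does not establish it. The time of entry is missing, and some of these events could come before it.
- **That direct extubation can occur only under usual care.** It is a departure in both groups, because controls are also due a T-tube SBT before extubation. Different adherence is possible, but the plan's sequence does not imply it.
- **That self-extubation will be commoner in the study group.** The airway score holds back only patients who do not reach the threshold. The study group also has a once-daily SBT, and the Introduction cites weaning protocols as shortening ventilation by 25% and weaning time by 78%. Time at risk could move either way.
- **That the death exclusion has the same fault.** It most plausibly acts before entry.

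It is also fair to say that failure after planned extubation only is a defensible outcome. It has to be declared in advance as the quantity of interest, not reached through an open-ended exclusion.

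**Conclusion.** The point holds as a defect of wording with a possible bias behind it. The three criteria, followed literally, can take entered patients out of the primary and mortality comparisons, against the stated analysis principle. Differential loss is possible, and its direction is unknown.

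The 0.7 to 8.5 points of spurious difference rest wholly on assumed frequencies, on losses confined to one group and on a higher failure risk among those lost than in the group as a whole. The corresponding chance of a significant result with no true effect is 5% to 29%. The upper end needs the most extreme combination; the middle case (10% lost, 50% failing) gives 2.7 points and 7%. The need for correction does not depend on these figures. If outcomes of excluded patients are not collected, the analysis cannot be repaired afterwards.

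**What to change.** 1. Define the time of entry and of group assignment, for example when the readiness conditions are met.
2. Limit the direct-extubation, self-extubation and transfer exclusions to events before that time.
3. Keep every entered patient in their group. After self-extubation or direct extubation, count failure by whether the patient failed. Add a sensitivity analysis restricted to planned extubations. State how entered patients who are never extubated count in the denominator.
4. Keep transferred patients with their recorded extubation result, and obtain hospital and 90-day status from the receiving hospital. Censor at transfer only in the Kaplan-Meier analysis, and only when status cannot be obtained. Censoring does not serve hospital mortality or hospital stay, which are compared with chi-square or Fisher and with t or Mann-Whitney tests, and transfer may itself be related to prognosis.
5. Report the number of each event by group.

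The cost is protocol wording, a count by group and status follow-up for transferred patients, which 90-day mortality already requires for discharged patients. The small downside is that some unplanned extubations enter the primary analysis; the sensitivity analysis shows their effect. The change does not remove confounding from non-randomised allocation.

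### Extubation failure, the primary outcome, has no criteria or time window, and the control-group rule on non-invasive ventilation contradicts itself, so controls rescued without reintubation may go uncounted

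*Combined protocol and SAP*

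**What the plan says.** The Introduction sets the aim: "The primary objective is to reduce the failure rate of extubation". Nothing there, or later, attaches clinical criteria or a time window to that outcome.

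The study-group section (Protocol study) lists criteria for a failed spontaneous breathing trial (SBT). For a failed extubation it says only "In case of extubation failure, the patient will be reintubated". It then excludes NIV in words that cover the whole study: "The use of non-invasive ventilation is not considered in this study (neither prevention of extubation failure nor in case of extubation failure".

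The control-group section (Conventional weaning) refers back: "The criteria for SBT and for extubation failure are the same than in the study group". Its next sentence is "In case of extubation failure, non-invasive ventilation will be not considered, but it left to the discretion of the attending physician".

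The Statistic Analysis section names the planning event differently: "the need for an intubation could be reduced by 13" percentage points, from 26% in controls to 13% in the study group, with 109 patients per group.

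The design is stated in Material and Methods: "A prospective interventionist no randomized study will be conducted in a medical-surgical ICU". No blinding is described.

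**The concern.** Two gaps meet at the primary outcome.

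First, the control-group section borrows its extubation-failure criteria from a section that contains none. Only SBT failure is defined there, and that is judged before extubation. Reintubation appears as the response to failure, not as its definition, and no period is given within which failure counts.

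Second, the rescue rule can be read as different in the two groups. A study patient who fails must be reintubated. A control who fails may, under the discretion clause, receive NIV and never be reintubated. Whether that control is a failure depends on a definition the plan does not give.

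If such controls are not counted, the control failure rate falls for a reason unrelated to the weaning protocol, and a real benefit is diluted. Because the study is neither randomised nor described as blinded, a counting rule left open could also be settled after group and outcome are known. That is a possibility; nothing in the documents shows that it happened.

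**Working it through.** **1. Reading the text.** Two readings are possible.

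- *Failure declared first.* The control sentence opens with the case of extubation failure, so the patient has already failed when NIV is chosen. If failure is declared on the same criteria in both groups, NIV does not change the count and every effect below is zero. This reading needs criteria that the plan does not supply.
- *Failure means reintubation.* The sample size is planned on the need for intubation. If that is the event and the discretion clause is followed, a control managed by NIV alone is not counted, while a similar study patient is reintubated and counted.

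**2. The plan's own figure.** Inputs from Statistic Analysis: 26% vs 13%, alpha 0.05, power 80%, equal groups, sidedness not stated. The unpooled normal formula is

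n = (z_alpha + z_beta)² × [p1(1−p1) + p2(1−p2)] / (p1−p2)²

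The variance term is 0.26×0.74 + 0.13×0.87 = 0.3055, and (p1−p2)² = 0.0169.

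- One-sided: (1.645 + 0.842)² × 0.3055 / 0.0169 gives 112, within 3% of the stated 109.
- Two-sided: (1.960 + 0.842)² × 0.3055 / 0.0169 gives 142.

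The stated 109 is therefore close only to a one-sided calculation. That is a separate matter. Power is given both ways below, and only the drop matters for this point.

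**3. Dilution (illustration).** Let r be the share of control reintubations that NIV averts. The documents give no NIV uptake or success rate, so r is assumed, and 26% is taken as a pre-NIV rate. The counted control rate is 0.26 × (1 − r). Power is the sum, over all pairs of counts in two binomials of size 109, of the probability of pairs that the uncorrected chi-square test rejects.

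| r (assumed) | Counted control rate | Difference from 13% | Two-sided power | One-sided power |
|---|---|---|---|---|
| 0 | 26.0% | 13.0 points | 69% | 79% |
| 5% | 24.7% | 11.7 points | 61% | 72% |
| 10% | 23.4% | 10.4 points | 52% | 64% |
| 20% | 20.8% | 7.8 points | 34% | 46% |

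**4. How few patients it takes.** The planned counts are 109 × 0.26 = 28.34 and 109 × 0.13 = 14.17, rounded to 28 and 14. With equal groups of 109 (218 in all), for x1 and x2 failures,

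X² = 218 × (x1 − x2)² / [(x1 + x2)(218 − x1 − x2)]

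- 28 vs 14: 218 × 196 / (42 × 176) = 5.78, two-sided p = 0.016 (Fisher 0.025).
- 26 vs 14: 218 × 144 / (40 × 178) = 4.41, p = 0.036 (Fisher 0.053).
- 25 vs 14: 218 × 121 / (39 × 179) = 3.78, p = 0.052 (Fisher 0.076).

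Reclassifying 3 controls (3/28, about 11% of control failures) crosses 0.05 with chi-square; 2 (2/28, about 7%) suffice with Fisher's test. The plan allows either test. These are implicit NIV rescue rates, so this step is an illustration too.

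**The case against.** The strongest reply is that the NIV conflict is a drafting slip. The study-group section bans NIV for the study as a whole, the control sentence itself begins by ruling NIV out, and a single ungrammatical clause points the other way. Even if that clause is followed, NIV comes after failure and the failure criteria are said to be common. The planning phrase is the only text set against this, and a need for intubation is not necessarily a performed one. This reading is fair and cannot be excluded. It does not close the point, because the common criteria it relies on are not written anywhere.

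A second reply is that the figures rest on unknowns. That stands. The 26% comes from a cited earlier study that is not part of the documents. If that rate already reflects discretionary NIV under usual care, there is no loss of power against plan, although the groups would still be rescued and counted differently. The p-value shift shows how sensitive 109 per group is to any two or three reclassified events; it is not peculiar to NIV.

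A reader might go further and infer that counting NIV-treated controls as failures could manufacture a benefit for the study group. The documents do not support that. Preventive NIV is excluded and the control sentence mentions NIV only after failure. A study patient meeting the same criteria would be reintubated and counted, so counting the NIV-treated control would equalise the groups. A false benefit needs a lower threshold for declaring failure in controls, which the text does not set.

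Nor does the missing window create a group difference by itself, since nothing suggests that it would differ between groups.

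**Conclusion.** The point holds in a limited form. The missing criteria and window are plain on the text. The NIV clause makes this more than missing detail: followed as written, with reintubation as the event, it leaves rescued controls uncounted and biases the comparison against the study group.

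The effect ranges from zero, if failure is declared on common criteria before NIV, to a loss of about 8 to 35 points of two-sided power (69% to 61% and to 34%) for assumed averted shares of 5% to 20%. One-sided, the loss is about 7 to 33 points (79% to 72% and to 46%). These figures rest on assumed rates and on 26% being a pre-NIV rate. The documents do not show that any control would receive NIV, so this should be corrected as an open rule and not reported as an established bias. Confidence is medium, because the harmless reading is plausible.

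**What to change.** - Delete the discretion clause in the control-group section, so that the plan's own study-wide rule (no NIV, reintubation on failure) applies to both groups.
- Define the primary outcome once for both groups: reintubation within one fixed window after first extubation, with the same written reintubation criteria. This matches the planning event. The investigators choose the window, before any outcome is reviewed.
- Record any NIV start in both groups. The data items in Material and Methods do not name it, though that list may not be complete. Report the composite of reintubation or NIV as a sensitivity analysis, so that any NIV given despite the rule is visible.

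The cost is protocol wording and one data item. The downsides are slightly less physician discretion in a usual-care control group and, if the window is short, a control event rate that may fall below the 26% used for planning.
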